## 7. HANDLING OF MISSING DATA

Not applicable.

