### 8.2.7. Efficacy Analysis

- **Response rate and clinical benefit rate**

The number and percentage of patients by best overall response, the response rate and its 95% confidence interval, and the clinical benefit rate and its 95% confidence interval will be tabulated in the safety analysis set and efficacy analysis set.

The response rate is defined as the percentage of patients whose best overall response is CR or PR.

The clinical benefit rate is defined as the percentage of patients whose best overall response is CR, PR, or SD.

The best overall response is defined as the best response among recorded overall response.

Table 1 of “New Guideline for the Assessment of Treatment Effect on Solid Cancer (Response Evaluation Criteria in Solid Tumors [RECIST] Guideline)–Japan Clinical Oncology Group [JCOG] version in Japanese” will be used for overall response, but overall response based on combinations of tumor response not corresponding to the table because of unknown data and no entry of data was uniquely defined. Therefore, the

tabulation analysis is not in complete compliance with the guideline and uses the guideline for reference.

**Table 1. Overall Response Based on Combinations of Tumor Response in Target and Non-target Lesions Including the Presence or Absence of New Lesions**

Target lesion	Non-target lesion	New lesion	Overall response
HCR	CR	Absent	CR
CR	IR/SD	Absent	PR
PR	Other than PD	Absent	PR
SD	Other than PD	Absent	SD
PD	Any response	Any response	PD
Any response	PD	Any response	PD
Any response	Any response	Present	PD

The following tumor response will be converted as shown by the arrow.

Non-target lesion: Absent → CR, not entered → IR/SD.

New lesion: Not entered → absent.

Overall response not corresponding to any combination in Table 1 after the above conversion will be considered as “unassessable.”

In addition, tabulation will be performed in the same manner by category shown below.

For items using reference laboratory test values, results using corporate reference values will be tabulated separately from results using institutional reference values as necessary.

- Site of metastasis [none, lung, liver, bone, lung + 1 organ, lung + 2 organs, lung +  $\geq 3$  organs,  $\geq 2$  organs other than lung, others];
- Whether criteria for proper use are met [yes, no];

- Prior treatment history [IFN- $\alpha$ , IL-2, Sutent, Nexavar, Afinitor, others];

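### Blank new-lesion and non-target boxes are scored as no progression, which can raise but never lower the response and clinical benefit rates relative to true status, and the visible SAP does not measure the effect

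*SAP*

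**What the plan says.** SAP 8.2.7 derives the overall response from three entries: target lesion, non-target lesion and new lesion. In its Table 1, target PD, non-target PD or a new lesion each makes the overall response PD.

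Two conversions come before the table is applied: "Non-target lesion: Absent → CR, not entered → IR/SD" and "New lesion: Not entered → absent". What still fits no row is set aside: "Overall response not corresponding to any combination in Table 1 after the above conversion will be considered as" unassessable. No conversion is given for a blank target box.

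The summary measures are then:

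- "The best overall response is defined as the best response among recorded overall response".
- For the response rate, a patient counts if that best result reaches CR or PR.
- "The clinical benefit rate is defined as the percentage of patients whose best overall response is CR, PR, or SD".

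Both rates "will be tabulated in the safety analysis set and efficacy analysis set". Section 5.2 removes unassessable patients from the efficacy set. The Version 3.0 entry in SAP Section 1 explains that the safety-set analysis was added so that these patients count as not responding and as having no benefit. SAP Section 7, on missing data, reads "Not applicable".

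**The concern.** A blank new-lesion box is unknown, not negative. Protocol 6.5.1 asks for all three lesion types to be assessed at Weeks 8, 16 and 24. The SAP itself separates a non-target entry of absent from one not entered, and converts them differently. Each blank is nevertheless given a value that rules out PD from that box.

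Response rate and clinical benefit rate are the main effectiveness items in Protocol 7.2.2. Because the best single record decides, and 8.2.7 counts any SD without a duration, one converted record is enough. A patient with target SD and a blank new-lesion box at Week 8, and fully recorded PD at Week 16, has a best overall response of SD and counts as a benefit. The exact confidence intervals of SAP 8.1.3 cover sampling error only and do not reflect this.

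**Working it through.** The documents state no expected rate and no share of blank boxes, so there is no planned figure to reproduce. The check has two parts: direction, then size under assumed counts.

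**Direction.** I applied Table 1 and the two conversions to every pattern with at least one of the two boxes blank.

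- Target: CR, PR, SD, PD or blank (5 states).
- Non-target (CR, IR/SD, PD, absent, blank) by new lesion (absent, present, blank): 5 × 3 = 15 pairs. Of these, 4 × 2 = 8 have both boxes filled, which leaves 7.
- Patterns to examine: 5 × 7 = 35.

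The PD rows were taken to apply whatever the other boxes contain, and a blank was taken to fit no other row.

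| Result | Patterns |
|---|---|
| PD with or without conversion | 15 |
| Unassessable either way (target also blank) | 5 |
| Unassessable, converted to CR | 2 |
| Unassessable, converted to PR | 8 |
| Unassessable, converted to SD | 5 |
| Unassessable, converted to PD | 0 |

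In all 15 converted patterns the blank could hide PD. In none does the conversion place a true CR or PR below PR, or a true CR, PR or SD below SD. With the same patients in the denominator, the error in both rates is therefore zero or upward.

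Twelve of the 15 have a blank new-lesion box; three (target CR, PR or SD) have only the non-target box blank. Table 1's PR and SD rows accept any non-target entry except PD. If a blank already satisfies that, the non-target conversion changes nothing for the PR and SD cases, and 13 patterns remain, 12 of them from the new-lesion rule.

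**Size, all counts assumed except the target of 600.** Take 600 patients in the safety set. Complete records give 40 CR/PR, 200 SD and 160 PD (400 patients). A further 60 have a known target response of CR, PR or SD and no usable record other than ones with a blank box. The other 140 are unassessable for other reasons. Let f be the share of the 60 whose true status is PD.

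| Clinical benefit rate (8.2.7 definition) | Efficacy set | Safety set |
|---|---|---|
| SAP conversion | 300/460 = 65.2% | 300/600 = 50.0% |
| Truth, f = 10% | 294/460 = 63.9% | 294/600 = 49.0% |
| Truth, f = 50% | 270/460 = 58.7% | 270/600 = 45.0% |
| Blanks unassessable | 240/400 = 60.0% | 240/600 = 40.0% |

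The overstatement is 60f/460 in the efficacy set (1.3 to 6.5 points for f = 10% to 50%) and 60f/600 in the safety set (1.0 to 5.0 points).

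For the response rate in the efficacy set, leaving blanks unassessable gives 40/400 = 10.0%. Conversion gives 40/460 = 8.7% if all 60 are target SD, 46/460 = 10.0% if 6 are CR/PR, 60/460 = 13.0% if 20 are, and 100/460 = 21.7% if all are.

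**The case against.** The strongest objection is that the alternative is biased too. Making a blank unassessable unless PD is already entered keeps incomplete PD records and drops incomplete non-PD ones, which pulls the rates down. With the counts above and f = 10%, the SAP rule misses the true efficacy-set benefit rate by +1.3 points and the alternative by −3.9. The two are equally far off at the midpoint:

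- Efficacy set: (65.2 + 60.0)/2 = 62.6% = (300 − 60f)/460, so f = 20%.
- Safety set: (50.0 + 40.0)/2 = 45.0% = (300 − 60f)/600, so f = 50%.

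Below those values the SAP rule is nearer the truth. This stands, and it is why the main rule should not be replaced.

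Other points have weight. The rule is prespecified, and 8.2.7 openly says that the analysis departs from the guideline. SAP Section 4 calls the study non-confirmatory. Protocol 5.5 lets the sponsor query forms, and SAP Section 9 plans a listing of tumor response. Parts of 8.2.6 and 8.2.7 are redacted or not available, so a sensitivity analysis there cannot be excluded. None of this measures the effect in the text that can be read. The planned extra tabulation concerning the determination of response does not mention undoing the conversion.

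A reader might infer more than the documents support:

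- **That missing data can only favor the drug.** A blank target box, with no PD entered elsewhere, stays unassessable and is a failure in the safety set. Target CR with a blank non-target box becomes PR, so a CR can be lost, although CR+PR is unchanged. Compared with leaving blanks unassessable, conversion can lower the efficacy-set response rate (10.0% to 8.7% above).
- **That the bias equals the share of blank boxes times the share hiding a lesion.** That product works on assessments. The rates use each patient's best response, so a patient with an equally good complete record is unaffected.
- **That PFS is inflated in the same way.** SAP 6.2 does not say that PD dates come from the converted responses.

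**Conclusion.** The concern holds in a limited form. For these two boxes, the conversions can overstate but not understate the response rate and clinical benefit rate relative to true status. The new-lesion rule carries most of the effect. Converted records bypass the safety-set analysis meant to guard against optimistic handling, and the visible SAP neither reverses the conversion nor counts the records affected.

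The size cannot be established from the documents. It is governed by the share of patients whose best overall response rests only on converted records and by how many of those had progressed. The 1.3 to 6.5 points (efficacy set) and 1.0 to 5.0 points (safety set) illustrate the arithmetic for assumed counts and are not an estimate. They use the 8.2.7 definition of clinical benefit; SAP 6.2 and Protocol 7.2.2 attach a 24-week condition to SD.

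This is a gap in transparency in a descriptive study. It does not show that the reported rates are wrong.

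**What to change.** Keep the present conversion as the main rule and add to SAP 8.2.7:

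1. A sensitivity run of the response and clinical benefit tables in both analysis sets, in which a record with a blank new-lesion or non-target box is unassessable unless the entered components already give PD. Patients left unassessable count as non-responders without benefit in the safety set.
2. The number of patients whose best overall response of CR, PR or SD depends on a converted blank, meaning that it changes when those records are set to unassessable.
3. A cross-reference from Section 7 to these rules.

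The cost is one extra run of existing tables. The sensitivity rates may be less favorable and may err downward, so the two runs should be read as a range. In the safety set they bracket the true rates as far as these two boxes are concerned. In the efficacy set the range is only indicative: with the counts above, the true benefit rate falls below the sensitivity result of 60.0% once (300 − 60f)/460 < 0.60, that is, f above 40%. The response rate there can move either way. If the count in item 2 is small, the question is closed.

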6.5 Effectiveness evaluation

6.5.1 Clinical evaluation of tumor

Clinical evaluation of tumor will be performed at Weeks 8, 16, and 24 after the start of administration. The presence/absence of the target, non-target, and new lesions will be evaluated at each evaluation time point. The evaluation will be performed using the following 4 classes with reference to the "New response evaluation criteria in solid tumours: Revised RECIST guideline (version 1.1) - Japanese Translation JCOG Version."

| | | |
|---------------------|------|---|
| Complete response | (CR) | Disappearance of all target regions |
| Partial response | (PR) | At least a 30% decrease in the sum of the longest diameter (LD) of target lesions, taking as reference the baseline sum LD |
| Progressive disease | (PD) | At least a 20% increase in the sum of the LD of target lesions, taking as reference the smallest sum LD recorded since the treatment started |
| Stable disease | (SD) | Neither sufficient shrinkage to qualify for PR nor sufficient increase to qualify for PD, taking as reference the smallest sum LD since the treatment started |

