## **5.2. Efficacy Analysis Set**

The efficacy analysis set basically consists of evaluable patients (patients considered to have undergone an appropriate evaluation).

However, patients who violate efficacy criteria among separately specified patient inclusion criteria will be excluded.

Not meeting conditions for target patients, experience of treatment with this drug, efficacy evaluation “unassessable” (not meeting conditions for assessment).

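### SAP 8.2.7 cannot score a patient with no target lesion as CR, PR or SD: the safety set counts such patients as failures, and the efficacy set may keep or drop them by outcome

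*SAP*

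**What the plan says.** SAP 8.2.7 derives overall response from three entries: target lesion, non-target lesion and new lesion. In Table 1, each row that yields CR, PR or SD requires CR, PR or SD for the target lesion. PD is reached through target PD, non-target PD or a new lesion; in the last two of these rows the target column reads 'Any response'.

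The conversions made before the table is applied are "Non-target lesion: Absent → CR, not entered → IR/SD" and "New lesion: Not entered → absent". Neither concerns the target lesion. Then: "Overall response not corresponding to any combination in Table 1 after the above conversion will be considered as" unassessable.

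On the rates, the SAP says: "The best overall response is defined as the best response among recorded overall response". It also says: "The clinical benefit rate is defined as the percentage of patients whose best overall response is CR, PR, or SD". The response rate counts CR or PR only. Both rates "will be tabulated in the safety analysis set and efficacy analysis set". The exclusions from the efficacy set in SAP 5.2 include "efficacy evaluation “unassessable” (not meeting conditions for assessment". The version 3.0 entry in SAP section 1 explains that the safety-set analysis treats unassessable patients as having neither response nor clinical benefit.

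Protocol section 2 takes in all treated patients and states no measurable-disease requirement. Protocol 6.5.1 adds: "The presence/absence of the target, non-target, and new lesions will be evaluated at each evaluation time point".

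**The concern.** A patient whose disease is entirely non-target has no row in Table 1 that leads to CR, PR or SD. The SAP provides for an absent non-target lesion but not for an absent target lesion. Because the surveillance sets no measurable-disease condition, such patients can be enrolled.

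In the safety set they remain in the denominator and can never enter the numerator. In the efficacy set, whether they are included may depend on the outcome being measured. The two rates are the main effectiveness items in protocol 7.2.2. SAP 8.2.7 also tabulates them by site of metastasis and tests them across demographic factors. If the share without a target lesion differs between categories, the scoring rule alone can create a difference.

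**Working it through.** The plan gives no numerical figure for either rate, so there is nothing to reproduce first.

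**Step 1: what Table 1 returns.** The first row's target entry is garbled in the text and is read here as CR. Each target state was combined with five non-target entries (CR, IR/SD, PD, absent, blank) and three new-lesion entries (absent, present, blank), giving 15 combinations. 'Any response' was taken to include no target lesion.

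| Target lesion | CR | PR | SD | PD | Unassessable |
|---|---|---|---|---|---|
| CR | 4 | 4 | 0 | 7 | 0 |
| PR | 0 | 8 | 0 | 7 | 0 |
| SD | 0 | 0 | 8 | 7 | 0 |
| PD | 0 | 0 | 0 | 15 | 0 |
| Absent | 0 | 0 | 0 | 7 | 8 |
| Blank | 0 | 0 | 0 | 7 | 8 |

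With no target lesion and no new lesion, non-target CR and non-target IR/SD are both unassessable.

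**Step 2: direction in the efficacy set on this reading.** Let n patients have a target lesion, x of them with benefit. Among patients without one, k have recorded PD (kept) and b do not (dropped). The reported rate is x/(n+k).

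- Compared with leaving all of them out, x/(n+k) is below x/n whenever k > 0 and x > 0. This holds for both rates.
- Compared with classifying them and counting the b patients as benefit, x/(n+k) is below (x+b)/(n+k+b) whenever b > 0 and x < n+k.
- For the response rate, classifying them raises the figure only if the share of non-target CR among the b dropped patients exceeds the rate in the set. That direction is therefore not fixed.

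**Step 3: size for the clinical benefit rate.** Assumptions, none from the documents: a share s without a target lesion; true control p = 60% with or without one; stable non-target disease counted as benefit; recorded PD in all the rest (r = 0.4). Efficacy-set rate = p(1−s)/[(1−s)+r·s]. Safety-set rate = p(1−s).

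| s | Efficacy set | Shortfall (points) | Safety set | Shortfall (points) |
|---|---|---|---|---|
| 2% | 0.588/0.988 = 59.5% | 0.5 | 58.8% | 1.2 |
| 5% | 0.570/0.970 = 58.8% | 1.2 | 57.0% | 3.0 |
| 10% | 0.540/0.940 = 57.4% | 2.6 | 54.0% | 6.0 |
| 20% | 0.480/0.880 = 54.5% | 5.5 | 48.0% | 12.0 |

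For example, with 540 patients with and 60 without a target lesion, the efficacy set gives 324/(540+24) = 57.4% and the safety set 324/600 = 54.0%, against 360/600 = 60.0%.

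**Step 4: sensitivity to recorded PD, at s = 10%.** If stable non-target disease at Week 8 is followed by PD at Week 16, the patient is scored unassessable and then PD, so r can exceed 0.4. With r = 0.7, the rate is 0.54/0.97 = 55.7% (4.3 points short). If some uncontrolled patients never have PD recorded, r is lower. With r = 0.2, it is 0.54/0.92 = 58.7% (1.3 points short).

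**Step 5: the other reading.** If patients without a target lesion are dropped whatever their outcome, the efficacy set gives 324/540 = 60.0%. The all-patient figure is (324+24)/600 = 58.0% if their benefit rate is 40%, and (324+48)/600 = 62.0% if it is 80%. The error can go either way. The safety-set figures do not change.

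**The case against.** The strongest reply is that outcome-dependent selection rests on one reading. Taken literally, a patient with no target lesion has no target response, so 'Any response' would not apply and progression would be unassessable too. SAP 5.2 also relies on separately specified criteria that are not shown, and part of the end of 8.2.7 is not in the available text. This stands as a limit. The wider reading is more natural, because the table uses the same phrase in the new-lesion column, where entries are only present or absent. It is not certain.

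Second, protocol 6.5.1 speaks of presence or absence at evaluation visits. An absent target lesion at Week 8 may be one that has disappeared, which the protocol calls CR. This also stands: the case report form coding is not shown, and any rule must separate the two situations.

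Third, counting unassessable patients as failures in the safety set is deliberate. That is a reasonable conservative choice for missing evaluations. It fits less well for a patient who was evaluated and did not progress. The SAP attributes its departure from the guideline to unknown or unentered data, and having no target lesion is neither.

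Fourth, the size is assumed and may be small. At 60% and 600 patients, the approximate 95% half-width is 1.96 × √(0.6 × 0.4/600) = 3.9 points, larger than the efficacy-set shortfall at s = 10%. SAP section 4 describes the study as not confirmatory, and 8.2.4 tabulates exclusions by reason. This limits the weight of the point, although a larger sample would not remove the error.

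Finally, a reader might infer that the reported clinical benefit rate is too low overall. The documents do not support that. Turning a blank non-target entry into IR/SD and a blank new-lesion entry into absent both push upward, as does 8.2.7 counting any SD when SAP 6.2 asks for SD of at least 24 weeks.

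**Conclusion.** The point holds as a gap in a stated scoring rule. Table 1 and its conversions offer no route to CR, PR or SD without a target lesion. In the safety set this lowers the response rate wherever non-target disease has disappeared. It lowers the clinical benefit rate wherever non-target disease has disappeared or, if stability is accepted as benefit, is stable. Neither depends on how 'Any response' is read.

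In the efficacy set, the downward pull on the clinical benefit rate holds on the more natural reading of the PD rows. If these patients are dropped regardless of outcome, the direction is uncertain. It would therefore go too far to state as fact that they enter only when they progress.

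The size cannot be fixed from the documents. The 0.5 to 5.5 points (efficacy set) and 1.2 to 12.0 points (safety set) rest on assumed shares of 2% to 20% and on the Step 3 assumptions. They describe this mechanism alone, not the net bias.

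**What to change.** Choose one rule for patients with no target lesion at baseline and apply it in both analysis sets.

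- **Classify them.** Add rows to Table 1: non-target CR with no new lesion is CR; non-target IR/SD with no new lesion is non-CR/non-PD, shown as its own category, with a stated rule on whether it counts as clinical benefit; non-target PD or a new lesion is PD. The separate category is needed because protocol 6.5.1 defines SD by target-lesion diameters.
- **Or exclude them at baseline.** Remove them from the denominators of both rates whatever their outcome, and report their number and outcomes separately.

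Under either option, state how a target lesion that disappeared on treatment (CR) is told apart from one that was never present, and say whether 'Any response' includes no target lesion. The cost is a little programming and either one extra response category or a slightly smaller denominator. No new data collection is foreseen, provided the recorded lesion data identify baseline target-lesion status.

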7.2.2 Analysis for effectiveness evaluation

The response rate and clinical benefit rate as shown below will be used as main analytical items in the effectiveness analysis set. An **CCI** analysis including the examination of factors influencing effectiveness will be performed, as required.

- [1] Response rate (rate of CR + PR)
- [2] Clinical benefit rate (Rate of cases with CR + PR + SD maintained for 24 weeks or longer)

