			
demographic.”
 
 
Section 8.2.6: “Incidence of adverse reactions by medical history, prior treatment history, and concomitant therapy” was added.
 
Section 8.2.6: The description “patients with special background” was changed to “subgroups.”
 
Section 8.2.6: Tabulation by presence/absence of treatment, the outcome of patients with CTCAE Grade 1 events, and the time course of CTCAE Grade were added to “further tabulation of interstitial lung disease.”
 
Section 8.2.6: “Further tabulation of diabetes mellitus/hyperglycemia” was added.
 
Section 8.2.6: “Further tabulation of hypercholesterolemia/hyperlipidemia” was added.
 
Section 8.2.6: “Further tabulation of infection” was added.
 
Section 8.2.6: “Further tabulation of mucositis-related adverse events” was added.
 
Section 8.2.6: “Further tabulation of skin disorder” was added.
 
Section 8.2.6: Tabulation of the duration of treatment was added to CCI analyses.
 
Section 8.2.7: Clinical benefit rate was added to the tabulation of response rate. In addition, the categories of each item were specified.
 
Section 8.2.7: Demographic items specified in “response rate by patient demographic” were moved to Section 10.1.1 “Patient demographics to be used to evaluate safety and efficacy.”
 
Section 8.2.7: “CCI tabulation analyses” was
 

Version	Date	Author(s)	Summary of Changes/Comments
			
added.
 
 
Section 10 [CC1] tabulation analyses" in the previous version was deleted, and the [CC1] tabulation analysis plan was moved to Section 8.2.6 and Section 8.2.7.
 
Other modifications of clerical errors and description adjustments were made.
 

3.0	15/SEP/2016	PPD	
 
Section 6.2: Progression-free survival (PFS) was added.
 
Section 8.1.4: The calculation of 95% confidence interval was added.
 
Section 8.2.7: An analysis in the safety analysis set was added to calculate the response rate and clinical benefit rate in the case where patients who were "unassessable" in the efficacy evaluation (patients excluded from the efficacy evaluation) are considered as patients who did not respond to treatment or did not achieve clinical benefit.
 
Section 8.2.7: The tabulation analysis of progression-free survival was added.
 

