## 6.2. Efficacy Endpoints

1. Response rate (percentage of complete response [CR] + partial response [PR])
2. Clinical benefit rate (percentage of CR + PR + stable disease [SD] for at least 24 weeks)
3. Progression-free survival (PFS): Time from the date of initiation of treatment with this drug in this study to the date progressive disease (PD) or all-causality death is first confirmed during the treatment period (including 28 days after the completion of treatment with this drug) and the period up to the date of final evaluation of tumor response. PD or death occurring during the treatment period (including 28 days after the completion of treatment with this drug) or the period up to the date of final evaluation of tumor response, whichever period is the earlier, will be handled as a PFS event, and patients without a PFS event will be censored at the date of final evaluation of tumor response. Patients with no record on tumor response at all will be censored at the date of initiation of treatment with this drug.

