- Baseline LDH (1.5-fold of institutional upper reference limit) [high value ( $>1.5$ -fold), normal ( $\leq 1.5$ -fold)];
- Baseline LDH (1.0-fold of institutional upper reference limit) [high value ( $>1.0$ -fold), normal ( $\leq 1.0$ -fold)].

In addition, the above tabulation will be performed using the best overall response as a study not requiring determination of CR and PD.

- Response rate and clinical benefit rate by patient demographic

The response rate and clinical benefit rate will be calculated by item listed in “[Section 10.1.1. Patient demographics to be used to evaluate safety and efficacy.](#)” For the response rate and clinical benefit rate, tests specified in [Section 8.1.3](#) will be performed between categories of each demographic factor.

For items using reference laboratory test values, results using corporate reference values will be tabulated in addition to results using institutional reference values.

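### SAP 6.2 can censor deaths before any tumour evaluation at Day 1 for PFS, and the by-demographic efficacy tests in SAP 8.2.7 name no analysis set, so unassessable patients may be left out

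*SAP*

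**What the plan says.** **PFS.** SAP 6.2, item 3, makes progression or all-causality death an event within a window. The window is the treatment period plus 28 days, or the period up to the final tumour evaluation, whichever is earlier. Patients without an event are censored at their final tumour evaluation. The paragraph ends: "Patients with no record on tumor response at all will be censored at the date of initiation of treatment with this drug".

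**Analysis sets.** SAP 5.2 removes from the efficacy set patients with "efficacy evaluation “unassessable” (not meeting conditions for assessment"). SAP 8.2.7 defines the term: "Overall response not corresponding to any combination in Table 1 after the above conversion will be considered as" unassessable. In the protocol, Section 7.2.2 sets the default: "The response rate and clinical benefit rate as shown below will be used as main analytical items in the effectiveness analysis set".

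**Overall rates.** SAP 8.2.7 says that best overall response, response rate and clinical benefit rate "will be tabulated in the safety analysis set and efficacy analysis set". The version 3.0 entry in SAP Section 1 explains the purpose of the safety-set analysis: unassessable patients "are considered as patients who did not respond to treatment or did not achieve clinical benefit". The same tabulation is repeated by site of metastasis, proper-use status, prior treatment and baseline LDH.

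**By-demographic analysis.** The next item of SAP 8.2.7 reads "The response rate and clinical benefit rate will be calculated by item listed in" Section 10.1.1, and applies the Section 8.1.3 tests to both rates. It gives no analysis set and no rule for unassessable patients. SAP Section 7, on missing data, is marked as not applicable.

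**The concern.** The first scheduled tumour evaluation is at Week 8 (Protocol 5.4). Patients who stop alive should be evaluated at discontinuation if they were not evaluated in the preceding 4 weeks. The patients likely to have no evaluation are therefore mainly those who die or are lost before the first one.

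For PFS, the final sentence of the definition appears to override the death rule for exactly these patients. An unscanned early death is among the worst outcomes PFS can record, and Day-1 censoring removes it from the estimate.

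For the factor tests, the protocol default would condition the comparison on having been assessed. ECOG PS and MSKCC risk appear only in the Section 10.1.1 analysis and could plausibly act in part through early death or loss. That part of their effect would be missing from the tests. Objective 1 concerns effectiveness under actual use, and Protocol Section 3 says that forms from patients who stop before 12 weeks are collected to evaluate effectiveness as well as safety.

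**Working it through.** **The plan's own figures.** The only sizing logic is for adverse events: 1 − 0.99^300 = 0.951, so 300 cases meet the 95% target (the minimum is 299), and 300 / 0.50 = 600 registered. Both reproduce. Neither bears on the efficacy tests, and the documents give no expected response, benefit or unassessable rate. Every such rate below is an assumption.

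**How many patients might be exposed.** Protocol Section 3 puts discontinuation by Week 12 at about 40% in clinical studies and assumes 50% here. At a constant hazard, the share off drug by Week 8 is 1 − 0.60^(8/12) = 28.9% to 1 − 0.50^(8/12) = 37.0%. This measures discontinuation, not unassessability, because the discontinuation evaluation should recover most patients who stop alive.

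**PFS under the literal rule.** Let a fraction d die early and unscanned, with no other censoring before 12 weeks. Censored at Day 1, they leave the risk set, so the estimate becomes S/(1 − d).
- d = 5%: 0.50/0.95 = 52.6%.
- d = 10%: 0.50/0.90 = 55.6%.

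On the median scale, take exponential PFS with a median of 4.0 months among assessed patients. If 10% are counted as immediate events, the median is 4.0 × ln(0.90/0.50)/ln 2 = 3.4 months. Day-1 censoring leaves it at 4.0.

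**Factor tests.** Inputs: two factor groups of 300 (the 600 target split equally, assumed) and a two-sided Fisher's exact test at 5% (SAP 4 and 8.1.3), with 4,000 simulated trials per scenario. The rate with failures counted is the rate among the assessed × (1 − unassessable).

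| Endpoint and rate among the assessed | Unassessable | Efficacy set: n, rejection | Failures counted: rates | Rejection |
|---|---|---|---|---|
| Benefit 60% v 60% | 5% v 15% | 285 v 255, 0.04 | 57% v 51% | 0.29 |
| Benefit 60% v 60% | 10% v 20% | 270 v 240, 0.05 | 54% v 48% | 0.30 |
| Benefit 60% v 60% | 10% v 30% | 270 v 210, 0.05 | 54% v 42% | 0.82-0.84 |
| Benefit 60% v 60% | 15% v 40% | 255 v 180, 0.04 | 51% v 36% | 0.96 |
| Benefit 60% v 50% | 10% v 30% | 270 v 210, 0.56 | 54% v 35% | over 0.99 |
| Response 10% v 10% | 10% v 30% | 270 v 210, 0.04 | 9% v 7% | 0.12 |

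When the factor acts only through early failure, the efficacy set has no difference to find and rejects in 3-5% of trials across the scenarios run. When benefit also differs among the assessed, the effect is weakened but still visible (0.56 against over 0.99). For response rate, little is lost because there is little power to begin with.

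**The case against.** **The set is inferred.** The SAP does not say that the by-demographic tests drop unassessable patients; it names no set. The item just before it uses both sets, and carrying both forward is a fair reading. Protocol 7.1 leaves details of the sets to the SAP. The sentence on influencing factors in Protocol 7.2.2 is partly redacted, names no set and applies only as required. This stands: the exclusion is what the protocol default would give, not a stated rule.

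**Early failures are not lost from the plan.** A reader might infer that they vanish. They do not. The overall rates are given in both sets, with unassessable patients counted as failures in the safety set. Proper-use status and three other items are tabulated the same way. Exclusions are listed with reasons (SAP 8.2.4), and baseline characteristics are shown in both sets. What remains open is the set for the tests, and for factors that appear only in Section 10.1.1.

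**The PFS sentence can be read more narrowly.** It follows the rule for event-free patients and may be meant only for those among them with no evaluation date. Unscanned deaths would then already be events. That reading is possible, but the sentence carries no such limit, and part of the event window depends on a final evaluation date that these patients lack. Nor does the rule reach everyone without a usable evaluation: it covers only patients with no tumour record at all.

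**The tests are not confirmatory, and counting missing scans as failures has its own bias.** Both points are true. They support showing both versions, not leaving the choice open.

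**Conclusion.** The point holds in two parts. In SAP 6.2, the Day-1 censoring rule, read literally, overrides the all-causality death rule for unscanned deaths and biases PFS upward. The bias is about 2.6 to 5.6 percentage points on a 12-week PFS of 50% if 5-10% die early and unscanned, which is an assumed range. In SAP 8.2.7, the by-demographic tests have no stated set. Under the protocol default, they would attenuate the clinical-benefit effect of factors that act partly through early failure, by an amount that depends strongly on the assumed gap in unassessable rates.

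A reader might go further and conclude that such factors would look neutral. That holds only if a factor acts solely through early failure, and the documents give no basis for assuming so. Nor does the power of 0.82-0.84 describe the study; it belongs to one assumed scenario, and a 10-point gap gives about 0.30. Whether PFS is compared by factor could not be checked, because the PFS tabulation that the version 3.0 entry adds to SAP 8.2.7 is not in the text available.

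**What to change.** **SAP 6.2.** Limit Day-1 censoring to patients with no tumour record who also did not die during treatment or the following 28 days. Count deaths in that window without a tumour record as PFS events on the date of death. Protocol 6.7 collects the date when death is the reason for discontinuation. For deaths within 28 days of stopping for another reason, the adverse event record is the likely source, so confirm that it yields a date.

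**SAP 8.2.7, by-demographic item.** State that the Section 10.1.1 tables and tests are run in the safety analysis set with unassessable patients as non-responders and as having no clinical benefit. Give the efficacy-set version alongside, and show the number unassessable in each category.

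**Cost.** Two wording changes and one further run using the handling already planned for the safety-set rates. Rates become slightly less favourable, and some counted failures will reflect missing scans rather than treatment failure; the per-category counts let a reader judge how many. Patients with no visit after the first dose are excluded from the safety set (SAP 5.1), so this change to the tests does not reach them and their number should be reported.
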